2. SCHEDULE OF ACTIVITIES (SOA)

Epoch	Procedure/Assessment	Treatment Phase										Follow-up End of Study ^b					
		Treatment Period 1					Treatment Period 2										
		Run-in		Period 1			Washout		Run-in								
Relative time (h)	Screening	D-1	D-2	D1	D2	D3	D4	At least 7 days	D-1	D1	D2	D3	D4				
Ambulatory visits	Screening	Pre-Dosing dose t0h	t3h	t4h	t12h	t24h	t36h	t48h	t72h	Pre-Dosing dose t0h	t3h	t4h	t12h	t24h	t36h	t48h	t72h
Stay in center	X	<							X	<						X	
Discharge									X							X	
Informed consent	X																
Sequence randomization																	
Inclusion and exclusion criteria	X			X												X ^c	
Demography ^d	X																
Medical history	X																
Alcohol history	X																
Smoking history	X																
Drug / alcohol / tobacco / substance usage ^e	X			X												X	
Prior medications / therapies / procedures	X			X													
COVID-19 vaccination status	X																
Height	X																
Weight	X			X												X	
Complete physical examination	X			X					X		X		X		X	X	
Vital signs ^f	X			X		X			X		X		X		X	X	

Epoch	Screening		Treatment Period 1								Treatment Phase								Follow-up				
	Procedure/Assessment	Screening	Run-in	Period 1				Washout				Run-in				Treatment Period 2				End of Study ^b			
Relative time (h)	D-21 to D-2	D-1	D1		D2	D3	D4	D1		D2		D3		D4		D1		D2		D3		D4	
			Pre-Dosing dose 0h	t3h	t4h	t12h	t24h	t36h	t48h	t72h		Pre-Dosing dose 0h	t3h	t4h	t12h	t24h	t36h	t48h	t72h				
Visual examination ^g	X	X				X		X		X		X		X		X		X		X		X	
Ophthalmologic examination ^h	X																					X	
Standard 12-Lead ECG ⁱ	X	X	X			X																X	
Standard cardiac echocardiography ^j	X																					X	
Hepatitis B surface antigen, hepatitis C antibody and HIV	X																						
COVID-19 test ^k	X	X																				X	
FSH and estradiol ^l	X																						
Pregnancy test ^m	X	X																				X	
Hematology ⁿ	X	X				X		X		X		X		X		X		X		X		X	
Clinical chemistry ^o	X	X				X		X		X		X		X		X		X		X		X	
Coagulation ^p	X	X				X		X		X		X		X		X		X		X		X	
Urinalysis ^q	X	X				X		X		X		X		X		X		X		X		X	
PK blood samples ^r																							
Concomitant medications/therapies	X																						
Adverse events ^s	X																						
Study treatment administration																							
Meals: B=Breakfast, Lu=Lunch, Di=Dinner ^t																							

<-----> ----->

Assess continuously

Assess continuously

- a. At least 7 days between P1D1 and P2D1.
- b. The end-of-study (EOS) visit [30 (\pm 3 days) after the last study treatment administration or discontinuation] must be done for all the included participants, except participants who did not receive any dose of study treatment, for whom the EOS visit is not required.
- c. For P2D-1: exclusion criteria and only inclusion criteria 7 (vital sign) and 8 (safety lab) will be checked. Clinical relevance of abnormal value could be discussed for the participant's participation in the second period of the trial. However, and among the exclusion criteria PR interval >220 ms is acceptable, if not clinically significant (NCS).
- d. Sex, age at screening, year of birth and ethnicity.
- e. Urine drug screen, alcohol breath test and urine cotinine test.
- f. Supine and standing systolic and diastolic BP and PR (after at least 5 minutes at rest in the supine position and after standing for 5 minutes), and body temperature. At screening visit and D-1, 3, supine BP measurements will be performed within 5 minutes. An average for each parameter (SBP, DBP, HR) will be obtained.
- g. Visual assessment (general inspection of the eyes, examination of motility and alignment, any visual disturbances such as blurred vision or loss of vision) to be performed on site by the Investigator.
- h. Full ophthalmologic examination by ophthalmologist to be performed at screening (within 2 weeks before randomization) and EOS (within 1 week up to EOS) and in case of emergency, including best corrected visual acuity for distance testing, optical coherence tomography and/or fluorescein angiography, slit lamp examination, intraocular pressure and fundoscopy with attention to retinal abnormalities.
- i. ECGs are to be performed in triplicate (conducted within approximately 5 to 10 minutes total time). ECGs should be performed before blood collection at equivalent nominal time points.
- j. Within 2 weeks before randomization.
- k. COVID-19 antigenic test is to be performed at screening and D-1 of each treatment period and at the EOS visit. COVID-19 polymerase chain reaction (PCR) test is to be performed on P1D-1, if required.
- l. For postmenopausal female participants, serum FSH and estradiol to be performed at screening to confirm postmenopausal status (except if the participant is treated with HRT).
- m. For all female participants, serum pregnancy tests are to be performed at screening, D-1 of each period and at the EOS visit.
- n. Erythrocytes (red blood cells, RBC), hematocrit, hemoglobin, platelets; leukocyte count with differential: basophils, eosinophils, lymphocytes, monocytes, neutrophils/absolute neutrophil count; RBC indices: mean corpuscular hemoglobin, mean corpuscular volume, reticulocyte/erythrocytes.
- o. ALT, albumin, ALP, AST, GGT, bicarbonate, bilirubin (total and indirect), urea, calcium, chloride, CK, creatinine, amylase, lipase, total cholesterol, glucose, lactate dehydrogenase, magnesium, potassium, sodium, total protein, uric acid.
- p. aPTT and prothrombin ratio.
- q. Urinalysis (dipstick: pH, glucose, protein, blood, ketones, bilirubin, urobilinogen, nitrites and leukocyte esterase) will be performed. In case of positive results for white blood cells, red blood cells and/or nitrites, urine will be sent to the laboratory for microscopy and culture. If there is an explanation for the positive dipstick results (e.g., menses), this will have to be discussed with the Sponsor and should be recorded, and there might be no need to perform microscopy and culture)
- r. Serial PK blood samples will be collected at pre-dose within 15 min before treatment administration (0h), and t+0.5, 0.75, 1, 1.25, 1.5, 2, 3, 4, 5, 6, 8, 10 and 12h post-dose, as well as at 24, 36, 48 and 72h post-dose. 1 min, 3 min and 5 min time windows will be authorized up to 0.75 h, up to 1.5 h and up to 12 h, respectively.
- s. All AEs are collected from when the participant first provides informed consent until the EOS visit [30 (\pm 3) days after the last study treatment administration or discontinuation].
- t. In addition, a snack will be provided in the afternoon of D1 and lunch will be provided on D2.

LIST OF ABBREVIATIONS

ACSF	Array clinical service form
ADME	Absorption, distribution, metabolism and excretion
ADR	Adverse drug reaction
AE	Adverse event
AESI	Adverse event of specific interest
ALP	Alkaline phosphatase
ALT	Alanine aminotransferase
ANSM	Agence Nationale de Sécurité du Médicament et des produits de santé (French Drug Agency)
aPTT	Activated partial thromboplastin time
ARS	Agence Régionale de Santé (Regional Health Agency)
AST	Aspartate aminotransferase
AUC	Area under the plasma concentration-time curve
AUC _{last}	Area under the plasma concentration-time curve from time of administration to the last observed plasma concentration
AUC _{inf}	Area under the plasma concentration-time curve from time of administration to infinity
B	Breakfast
BE	Bioequivalence
BID	Twice daily (bis in die)
BMI	Body mass index
BP	Blood pressure
bpm	Beats per minute
BRAF	Virus-induced rapidly accelerated fibrosarcoma murine sarcoma viral oncogene homolog B
°C	Degree Celsius
CDER	Food and Drug Administration Center for Drug Evaluation and Research
CI	Confidence interval
CK	Creatine kinase
CL/F	Apparent total body clearance
C _{max}	Maximum observed plasma concentration
COVID-19	Coronavirus disease 2019
CPMP	Committee for Proprietary Medicinal Products
CPP	Comité de Protection des Personnes (Independent Ethics Committee)

CRA	Clinical research associate
CSR	Central serous retinopathy; or Clinical study report
CTD	Clinical Trial Document
CVintra	Intra-individual variations
CYP	Cytochrome P450
D	Day
Di	Dinner
ECG	Electrocardiogram
eCRF	Electronic case report form
EDC	Electronic data capture
e.g.	Exempli gratia (for example)
EMA	European Medicines Agency
EOS	End-of-study
ERK	Extracellular signal-regulated kinase
etc.	Et cetera (and the rest)
EudraCT	European Clinical Trials Database
FDA	Food and Drug Administration
FSH	Follicle stimulating hormone
GCP	Good Clinical Practice
GGT	Gamma-glutamyltransferase
GLP	Good Laboratory Practice
hCG	Human chorionic gonadotropin
H	Hour
HBs Ag	Hepatitis B surface antigen
HCV Ab	Hepatitis C virus antibody
HIV	Human immunodeficiency virus
HR	Heart rate
HRT	Hormone replacement therapy
ICF	Informed consent form
ICH	International Council on Harmonization
i.e.	Id est (that is)
IEC	Independent Ethics Committee
IOP	Intraocular pressure
IRPF	Institut de Recherche Pierre Fabre
IV	Intravenous

K2EDTA	Dipotassium ethylenediaminetetraacetic acid
kg	Kilogram
L	Liter
LLOQ	Below the lower limit of quantification
Lu	Lunch
LVEF	Left ventricular ejection fraction
λ_z	Apparent terminal elimination rate constant
m^2	Square meter
MedDRA	Medical Dictionary for Regulatory Activities
MEK	Mitogen-activated protein kinase kinase
mg	Milligram
min	Minute
mIU	Milli-international unit
mL	Milliliter
mmHg	Millimeter of mercury
MRT	Mean residence time
msec	Millisecond
NCI-CTCAE	National Cancer Institute - Common Terminology Criteria for Adverse Events
NCSF	Novartis clinical service form
NCS	Not clinically significant
ng	Nanogram
NOAEL	No observed adverse effect level
OTC	Over-the-counter
P	Period
P3-MI	Phase 3-market image
PCR	Polymerase chain reaction
PCSA	Potentially clinically significant abnormal(ity)
pg	Picogram
PK	Pharmacokinetics
PR	Pulse rate
QTcF	QT interval corrected using Fridericia's method
R	Reference
RAF	Rapidly accelerated fibrosarcoma
RAS	Rat sarcoma virus

RBC	Red blood cell (erythrocyte)
RVO	Retinal vein occlusion
SADR	Serious adverse drug reaction
SAE	Serious adverse event
SAP	Statistical analysis plan
SD	Standard deviation
SEM	Standard error of the mean
SoA	Schedule of activities
SUSAR	Suspected unexpected serious adverse reaction
t	Time
T	Test
$t_{1/2}$	Terminal elimination half-life
T_{last}	Time of last observed plasma concentration
T_{max}	Time to reach C_{max} (time at peak plasma level)
TEAE	Treatment-emergent adverse event
TOST	Two one-sided t-test
UGT1A1	Uridine diphosphate glucuronosyltransferase 1 family, polypeptide A1
ULN	Upper limit of normal range
Vz/F	Apparent volume of distribution
WOCBP	Woman of childbearing potential
WHO	World Health Organization
WMA	World Medical Association

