9.4. Adverse Events and Serious Adverse Events

The definitions of an AE or SAE can be found in [Appendix 2](#).

AEs will be reported by the participant (or, when appropriate, by a caregiver, surrogate, or the participant's legally authorized representative).

The Investigator and any qualified designees are responsible for detecting, documenting, and recording events that meet the definition of an AE or SAE and remain responsible for following up AEs that are serious, considered related to the study treatment or study procedures, or that caused the participant to discontinue the study (see [Section 8](#)).

The records of AEs must describe the nature (diagnosis, signs and symptoms), severity, date/time of onset, date/time of end, outcome and actions taken with study treatment, and relationship to study treatment (in the Investigator's opinion). It must be specified whether the event is serious or not and if yes, at least one seriousness criterion must be specified. The severity of AEs will be evaluated using the National Cancer Institute - Common Terminology Criteria for Adverse Events version 5.0 (NCI-CTCAE V5.0 [[15](#)]).

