9.4.3. Follow-up of AEs and SAEs

After the initial AE/SAE report, the Investigator is required to proactively follow each participant at subsequent visits/contacts. All SAEs (as defined in [Appendix 2](#)), will be followed until resolution, stabilization, the event is otherwise explained, or the participant is lost to follow-up (as defined in Section [8.4](#)).

Follow-up of AEs and SAEs

- The Investigator is obligated to perform or arrange for the conduct of supplemental measurements and/or evaluations as medically indicated or as requested by the Sponsor to elucidate the nature and/or causality of the AE or SAE as fully as possible. This may include additional laboratory tests or investigations, histopathological examinations, or consultation with other health care professionals.
- If a participant dies during participation in the study or during a recognized follow-up period, the Investigator will provide the Sponsor with a copy of any *post-mortem* findings including histopathology.
- New or updated information will be recorded using a new SAE form.
- The Investigator will submit any updated SAE data to the Sponsor's Corporate Vigilances Division within 24 hours of receipt of the information.

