9.5.2. Visual and Ophthalmological Examinations

9.5.2.1. Visual Assessment

Visual assessment (general inspection of the eyes, examination of motility and alignment, any visual disturbances such as blurred vision or loss of vision) will be performed on site by the Investigator.

The timing of the assessments is summarized in Section 2 (SoA).

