For all parameters and for participants with retest values, the last non-missing value will be used for the measurement time before the first IMP administration within each period (provided it was measured before IMP administration within each period) and the first non-missing value will be used for the measurement time after the first IMP administration within each period.

Unscheduled visits will not be analysed but presented in listings only.

Handling of incomplete dates

No management of incomplete dates will be performed. The incomplete dates will be labelled as such in the listings.

Baseline definition

For all parameters, baseline will be defined as the last available assessment prior to the first IMP administration within each period, including additional assessments (where applicable). Assessments that occurred on the same day as first dose, when time of assessment is not available, will be assumed to be prior to first dose.

Duration

Duration (in days, hh:mm) will be calculated by the difference between the start and stop date and time (e.g. duration of AE (days, hh:mm) = end of AE date and time - AE onset date and time).

Duration (in days) will be calculated by the difference between the start and stop date + 1 (e.g. duration of a medication (days) = end of medication date - onset of medication date + 1).

Type I error rate

Unless stated otherwise, statistical tests will be two-sided and will be carried out at the 5% level of significance.

7. *Description of study participants*

7.1. *Definition of analysis sets*

The following analysis sets will be defined:

Enrolled set: all participants who signed the ICF for the study.

Screened set: all enrolled participants having successfully completed the screening period.

Randomized set: all randomized participants.

Safety set: all included participants having taken at least one dose of study treatment, including those who did not complete the study.

Pharmacokinetic set: all of the participants who have taken one dose of study treatment in the two periods without any event (including no vomiting within 4 hours after dosing) and/or important protocol deviation affecting PK evaluation, with complete PK profiles in these two periods, i.e. sufficient PK concentration data to support the calculation of primary PK criteria (see section 9.1).

The analysis sets will be precisely defined and validated during the data review meeting and prior to database lock..

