8.4. Prior and concomitant medications

Information on prior and concomitant medications will be coded according to the WHO Drug Dictionary version of March 2022 (B3 with primary ATC selection).

A prior medication will be defined as a medication stopped prior to the date and time of the first administration of IMP. Prior medications are recorded in the “Concomitant medication” eCRF page and identified by the “Taken prior to treatment start” variable.

A concomitant medication will be defined as a medication that is taken by participants any time during the treatment period (on or after the date and time of first IMP administration for each participant). If the date value does not allow allocation of a medication to the prior or concomitant category (missing or incomplete start or end date), this medication will be considered concomitant.

A table with the number and percentage of participants having taken at least one previous medication and a table with the number and percentage of participants having taken at least one concomitant medication will be generated by sequence and overall (overall and by medication class [2nd level of Anatomical Therapeutic Chemical (ATC)] and medication drug name). Prior and concomitant medications will be listed separately.

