11.1. Adverse events

Adverse events, including pre-treatment events, will be recorded from the time of consent through until the EOS visit.

A treatment-emergent adverse event (TEAE) is an adverse event that starts or worsens during the on-treatment period. All analyses described in section 11.1 will be based on TEAEs if not otherwise specified.

The following treatment periods will then be considered:

Period	Start date/time	End date/time
Before any treatment	Date/time of inform consent	Date/time of first IMP administration of period 1 - 1 minute
Treatment 1	Date/time of first IMP administration of period 1	Date/time of first IMP administration of period 2 - 1 minute
Treatment 2	Date/time of first IMP administration of period 2	Date of end of study

Adverse events will be summarized by worst grade according to the National Cancer Institute - Common Terminology Criteria for Adverse Events version 5.0 (NCI-CTCAE V5.0 [5]) per participant and coded using MedDRA Version 24.0.

A summary table will present the number and percentage of participants with a TEAE overall and by formulation, including:

- TEAEs;
- TEAEs, grade ≥ 3 ;
- Related TEAEs;
- Related TEAEs, grade ≥ 3 ;
- TEAEs leading to any dose reduction;
- Related TEAEs leading to any dose reduction;
- TEAEs leading to permanent treatment discontinuation;
- Related TEAEs leading to permanent treatment discontinuation;
- Serious TEAEs;
- Related serious TEAEs;
- TEAEs leading to death;
- Related TEAEs leading to death.

Treatment-emergent adverse events will be summarised in tables as follows [overall and by SOC and PT]:

- Number and percentage of participants with at least one TEAE and number of occurrences of a TEAE by formulation and overall,
- By worst NCI-CTCAE grade, with the number and percentage of participants with at least one TEAE and number of occurrences of a TEAE by formulation and overall,
- By causality to study treatment, with the number and percentage of participants with at least one TEAE and number of occurrences of a TEAE by formulation and overall.

If there are only a few treatment-emergent adverse events (≤ 10), only a listing will be generated.

Additionally, AEs related to COVID-19 will be summarised by formulation and overall and listed separately. If there are only a few adverse events related to COVID-19 (≤ 10), only a listing will be generated.

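### A symptom-free retinal finding first seen at the end-of-study eye examination cannot be tied to either dose, yet SAP 11.1 has no category for it and, if it is dated at detection, counts it under the period 2 formulation

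*Protocol*

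**What the plan says.** **Retinal examination.** Footnote h to the schedule in Protocol section 2 places the ophthalmologist's examination, which includes fundoscopy and optical coherence tomography and/or angiography, "to be performed at screening (within 2 weeks before randomization) and EOS (within 1 week up to EOS) and in case of emergency". The copy of the schedule in SAP Appendix 1 has a shorter screening window but the same two scheduled occasions.

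**Eye checks between the doses.** The investigator's visual examination takes place at 24 h and 72 h after each dose and on the day before the period 2 dose. Protocol 9.5.2.1 defines it: "Visual assessment (general inspection of the eyes, examination of motility and alignment, any visual disturbances such as blurred vision or loss of vision". Nothing in that list, or in the physical examination of Protocol 9.5.1, is described as viewing the retina.

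**Adverse event records.** Protocol 9.4: "The records of AEs must describe the nature (diagnosis, signs and symptoms), severity, date/time of onset". Under Protocol Appendix 2, an abnormal safety assessment is an adverse event when the investigator considers it clinically significant.

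**Allocation to a formulation.** SAP 11.1: "A treatment-emergent adverse event (TEAE) is an adverse event that starts or worsens during the on-treatment period". The Treatment 2 window opens at "Date/time of first IMP administration of period 2" and closes at the end of the study. Treatment-emergent events (TEAEs) are tabulated by formulation and overall.

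**Unclear dates.** SAP section 6: "No management of incomplete dates will be performed". For medications, SAP 8.4 supplies a default, opening with "If the date value does not allow allocation of a medication to the prior or concomitant category (missing or incomplete start or end date" and then treating the medication as concomitant. Adverse events have no counterpart.

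**Examination results.** Protocol 10.2.7.2 describes screening and EOS measurements overall. SAP 11.3.4.2 lists the ophthalmologic results.

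**The concern.** Retinal events are a named risk of this drug class (Protocol 3.2.5 and 3.3.1). They underlie several exclusion criteria and one of the individual stopping rules in Protocol 8.2. The secondary safety objective compares the Test tablet with the Reference.

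A finding that causes symptoms after dose 1 can be examined and assigned correctly. Footnote h allows an emergency examination, and Protocol 9.4.3 adds "The Investigator is obligated to perform or arrange for the conduct of supplemental measurements and/or evaluations as medically indicated". A symptom-free change gives no reason to look. It is first seen after both doses, and the examination cannot say which dose preceded it. The per-period baseline in SAP section 6 does not help, because without an unscheduled examination both periods fall back on the same screening examination.

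The plan treats EOS measurements as belonging to no single formulation, but the TEAE windows do not carry that over. An event whose only known date is the EOS examination falls into Treatment 2 because of when it was found. At stake is whether the by-formulation columns can be read as tablet against tablet for these findings.

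**Working it through.** The plan states no figure here, so the check compares the examination times with the windows and then asks what the windows do to expected counts.

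**Timing.** EOS is 30 ± 3 days after the last dose, that is day 27 to 33. The examination falls within the week up to EOS.
- After dose 2: 27 − 7 = 20 days to 33 days.
- After dose 1, at the 7-day minimum interval: 20 + 7 = 27 days to 33 + 7 = 40 days.

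**Conditions for wrong assignment.** All must hold: the change follows dose 1; it causes no symptoms; it is still visible at EOS; it is judged clinically significant; and it is dated at detection. Neither document states the last as a convention.

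**Expected counts.** Assume 20 participants per sequence (40 planned, two sequences) and that all these conditions other than timing are met. Let pT and pR be the per-dose risks on Test and Reference, p = pT + pR, and g1 and g2 the shares of period 1 and period 2 lesions still visible at EOS.
- Counted Test (sequence RT) = 20(pT·g2 + pR·g1)
- Counted Reference (sequence TR) = 20(pR·g2 + pT·g1)
- Counted difference = 20(pT − pR)(g2 − g1)
- True difference = 40(pT − pR), so the fraction kept = (g2 − g1)/2
- Share under the wrong tablet = g1/(g1 + g2)

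**Equal persistence (g1 = g2 = g).** Both counts equal 20·p·g for any true split, and half of the counted findings are under the wrong tablet.

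**Illustration.** The documents give no rate of symptom-free findings. The pilot (Protocol 3.2.5) had one retinal event in 14 participants over both doses: 7.1%, exact 95% CI 0.18% to 33.87%. Borrowing p = 1/14, the number in 40 participants is 40/14 = 2.9 (interval 0.07 to 13.5).

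| True Test v Reference | Counted, g = 1 | Counted, g = 0.5 | Counted, g = 0 |
|---|---|---|---|
| 2.9 v 0 | 1.4 v 1.4 | 0.7 v 0.7 | 0 v 0 |
| 2.1 v 0.7 | 1.4 v 1.4 | 0.7 v 0.7 | 0 v 0 |
| 1.4 v 1.4 | 1.4 v 1.4 | 0.7 v 0.7 | 0 v 0 |

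At g = 1, the interval for each count is 20 × 0.0018 = 0.04 to 20 × 0.3387 = 6.8.

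**Unequal persistence.** Suppose lesions resolve exponentially at rate k, with interval w between doses and the examination on day d after dose 2. Then g2 − g1 = exp(−kd) − exp(−k(d + w)), which is largest at k = ln((d + w)/d)/w.

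| w (days) | d (days) | g2 | g1 | Largest fraction of true difference kept |
|---|---|---|---|---|
| 7 | 20 | 0.424 | 0.314 | 5.5% |
| 7 | 33 | 0.404 | 0.333 | 3.5% |
| 14 | 20 | 0.469 | 0.276 | 9.6% |
| 14 | 33 | 0.434 | 0.305 | 6.5% |

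In the first row, the share under the wrong tablet is 0.314/(0.314 + 0.424) = 43%, so half is an upper limit when later lesions are more often visible.

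**The case against.** The strongest reply is that several conditions must coincide and the documents establish none of them as likely. Protocol 3.3.1 considers such events unlikely after single doses. The investigator must date onset, not detection, and weigh the temporal relationship, so an onset other than the EOS date may be recorded. This stands: assignment to period 2 is conditional.

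The counts also rest on a borrowed rate. The pilot event was of moderate severity and resolved spontaneously. The text does not say how it was found, after which dose it arose or whether it caused symptoms. A reader might infer that about three symptom-free findings should be expected. The documents do not support that.

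Equal counts are an expectation, not a forecast. With three findings split at random, all three fall on one side with probability 2 × 0.5³ = 25%. So few events could not compare the tablets even if perfectly attributed. If the tablets carry equal risk, which is plausible for the same substance at the same dose with pilot exposure ratios of 0.98 to 1.05, the expected difference is zero both in truth and as counted.

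The plan also limits the effect. SAP 11.1 has an overall column and produces only a listing when there are 10 or fewer TEAEs. All adverse events and ophthalmologic results are listed, and incomplete dates are labelled in the listings. A careful reader could see that a finding was made at EOS.

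What remains is that the tables, if produced, have no place for an event that belongs to neither formulation, and the SAP is silent when onset is unknown.

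**Conclusion.** The point holds in a limited form and is minor. No scheduled retinal examination separates the doses. A symptom-free finding first seen at EOS and dated there is counted under the period 2 formulation without evidence for that tablet; with unknown onset it has no rule. For findings that persist to EOS, the expected comparison is pulled towards equality, and up to about half may be under the wrong tablet. This assumes balanced sequences, dating at detection and period 1 lesions no more often visible at EOS than period 2 lesions. The number of such findings is unknown and may be zero.

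Three stronger readings are not supported.
- That the SAP will misassign retinal events generally: findings with symptoms can be examined and assigned between doses, and findings that resolve before EOS are not counted at all.
- That the rule favours the Test tablet: with balanced sequences it favours neither, and only blurs a difference if one exists.
- That the Protocol section 4 endpoint wording or the recheck of exclusion criteria before period 2 (footnote c) must change: these are wording matters that alter no result. The 3-week binimetinib washout note in criterion 25 reads as an entry condition, so it does not bar participants from period 2.

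The bioequivalence analysis is untouched.

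**What to change.** Change SAP 11.1 only. For participants who received both doses, keep retinal findings first detected at the EOS ophthalmologic examination, without earlier symptoms or an earlier emergency examination, in the overall TEAE column. Show them in a separate row or column labelled as not attributable to a formulation. Findings with symptoms or an examination before the period 2 dose stay with the period 1 formulation.

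The cost is one rule and one extra table row or column, with no added visit, procedure or sample. The downside is that some events that truly arose in period 2 leave the by-formulation columns; under equal persistence that is half of those moved. They remain in the overall column and the listings. A retinal examination between doses would address attribution directly, but it is an added procedure for the sponsor's safety physicians to consider and is not needed for this fix.
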